PROTOCOL NARRATIVE

University of California, Irvine Institutional Review Board

Version: March 2006

HS#: 2006-5138 For IRB Office Use Only

Lead Researcher Name: [name]

Title: Evaluation of the Candela 1064nm Nd:YAG laser for Treatment of Cellulite and Tightening of Skin

Important: Please read the instructions before completing this protocol narrative.

NON-TECHNICAL SUMMARY

Provide a non-technical summary of the proposed research project that can be understood by IRB members with varied research backgrounds, non-scientists and community members. The summary should include a brief statement of the purpose of the research and related theory/data supporting the intent of the study and a brief description of the procedure(s) involving human subjects. *This summary should not exceed more than ½ a page*.

At present, there are no proven effective means for managing cellulite. There are two devices that have received FDA clearance for "temporary reduction in the appearance of cellulite". One is a mechanical massage machine (Endermologie, LPG, Fort Lauderdale, FL) under 510(k) K990445 and the other is the Velasmooth (Syneron Medical Ltd. Israel) under 510(k) K050397.

Non-ablative laser and light treatments are becoming an increasingly popular procedure. Non-ablative treatments have been shown to improve rhytides, pilosebaceous changes, pigmentary skin alterations and vascular lesions including facial telangiectasias and diffuse redness and are attractive to physicians and subjects because of minimal or no healing time, reducing subject inconvenience and risk.

It is our hypothesis that creating deep fibrosis in the skin will improve the appearance of cellulite. The laser used in this study will allow deep tissue heating, while using a cooling device to protect the outer layers from damage.

Approved by IRB on: 05/08/2009 HS# 2006-5138 Void After: 05/07/2010

IRB USE ONLY - DO NOT ALTER THIS FOOTER

e-CPA# 5126 1 of 20

SECTION 1: PURPOSE AND BACKGROUND OF THE RESEARCH

- 1. Describe the **purpose of the research** project and state the overall objectives, specific aims, hypotheses (or research question) and rationale for performing the study.
- 2. Provide the **relevant background information** on the aims/hypotheses (or research question) to be tested and the procedures/products/techniques under investigation.
- 3. Include a description of the predictor and outcome variables, as appropriate.
- 4. Include a critical evaluation of existing knowledge, and specifically identify the information gaps that the project intends to address.
- 5. Describe previous research with animals and/or humans that provides a basis for the proposed research. Include references/citations, as applicable.

There are numerous therapies that have been advertised for the treatment of cellulite, but there is little scientific evidence that any of these treatments are beneficial. In fact, much of this evidence is subjective or based upon patient self-assessment. The objective of this investigation is to evaluate safety and effectiveness of a non-ablative treatment for cellulite in conjunction with skin tightening by increasing dermatofibrosis of the reticular dermis using the Candela GentleYAG laser.

Study outcome will be assessed as follows:

A panel of three independent, blinded individuals experienced in dermatological cosmetic therapy will determine percent improvement in cellulite appearance by comparing photographs taken at the pretreatment visit to those from the 1, 3 and 6 month follow-up visits. Each evaluator will be ask to compare the treated and non-treated areas on a blinded basis and then will rate improvement on the scale 0 to 4, as described below.

% Improvement Description		core
0%	No improvement	0
1-25%	Slight improvement	1
26-50%	Moderate improvement	2
51-75%	Significant improvement	3
76-100%	Complete improvement	4

The difference scores between the treated and the untreated sides will be used to measure treatment efficacy.

The investigator's assessments during follow-up visits will be tabulated and analyzed with basic descriptive statistical methods.

Ultrasound analysis, skin elasticity measurements and non-invasive optical measurements may also be performed prior to treatment and at the 1, 3 and 6 month follow-up visits to determine any changes in skin thickness.

Safety will be assessed by clinical evaluation of purpura, edema, erythema, hyperpigmentation, hypopigmentation, blistering and scarring. Assessments will be performed by the investigator using the following scale:

0 = absence 1 = mild 2 = moderate 3 = severe

SECTION 2: ROLES AND EXPERTISE OF THE STUDY TEAM

List all study team members below.

- Describe their specific role and responsibility on the study in the text box provided.
- 2. **Faculty Sponsors** list as Co-Researchers and describe their role on the project; include oversight responsibilities for the research study.

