This is an open label trial. Treatment will be conducted on either the left or right knee, thigh, arm, or ½ the abdomen, depending upon which area has the most cellulite or skin laxity. The contra-lateral side will not be treated and will serve as a control. A comparison of baseline photographs (prior to treatment) to photographs taken 1, 3 and 6 months after the completion of treatment will be conducted. Photographic equipment and the protocol for photography will be consistent at each visit. Ultrasound may be taken at baseline and at the follow-up visits to evaluate flatness of cellulite and dermal fibrosis or enlargement of the reticular dermis. Non-invasive light measurements may also be taken at baseline and follow-up visits. These do not hurt or pose a risk to the subjects and are similar to shining a flashlight on the skin and measuring the light. The area treated will be measured with a tape measure, weight/height will be recorded and the Body Mass Index (BMI) will be calculated at baseline and follow-up visits. In addition, skin elasticity may be measured at the treatment areas at baseline and follow-up visits. The photographs, ultrasound and measurements will be taken using consistent procedures at each visit by viewing the baseline photograph and using landmarks such as freckles and birthmarks.

The laser system to be used in this clinical study, Candela GentleYAG, a 1064 nm Nd:YAG laser is a commercially available laser and has been cleared by FDA under K022923, K022951, K023193 and K033172.

The Candela GentleYAG is cleared for removal of unwanted hair, for stable long term or permanent hair reduction and for treatment of pseudofolliculitis barbae, and is indicated on all skin types Fitzpatrick I-VI including tanned skin. The GentleYAG is cleared for treatment of vascular lesions such as port wine stain birthmarks, telangiectasia, rosacea, and leg and spider veins, and is cleared for treatment of benign pigmented lesions such as lentigos (age spots), café au lait birthmarks, and tattoos. The laser is also indicated for treatment of red pigmentation in scars with vascularity, and for treatment of wrinkles.

The Candela DCD produces a brief, timed spray of cryogenic fluid that evaporates from the skin surface and cools the epidermis, prior to each laser pulse. The DCD has been cleared by the FDA for minimizing pain and cooling the epidermis during laser treatment (K953412). The DCD is part of the Candela GentleYAG laser system.

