- 8. The pre-treatment photographs will be obtained using the Canfield Monostand device. This device will keep the ambient lighting, background, camera settings exactly the same for each scheduled photograph during the study. Photographs will be of the treated and control areas.
- 9. Optional: Imaging of skin via a non-invasive high frequency ultrasound imaging device may be performed
- 10. Optional: Measurement of skin elasticity using non-invasive instrumentation may be performed.
- 11. Just prior to treatment, the subjects will be assigned a study subject number. These numbers will be assigned consecutively.

Laser Treatment:

[figure not shown]
One laser treatment will be performed, and the procedure will be as follows:

- 1. The treatment area will be photographed prior to the treatment. Emphasis will be placed on keeping the ambient lighting, background, camera settings exactly the same for each scheduled photograph during the study.
- 2. Tape measurement and weight will be recorded.
- 3. The treatment area will be comprised of the arm (circumferential upper arm area), knee (approximately 10cm circumferentially around the patellar bone), entire thigh (from the upper lateral areas of the thighs inner to outer area excluding hips moving downwards until just above the knee), or abdomen (from the costal margin to just superior to the pelvic bone).
- 4. Topical anesthetic may be applied to the skin according to the manufacturer's instructions if the subject requires it or if the doctors feels the subject might not tolerate the treatment with out the use of topical anesthetic
- 5. Starting with the selected diameter spot size handpiece, test spots may be conducted with the laser at a low fluence until the optimum fluence is achieved (prior to intolerable discomfort or a reaction of mild redness or edema is visible).
- 6. Laser treatment will include up to six (6) consecutive passes of the laser over the treatment area. The treatment parameters are noted in the following table.

Parameter	Parameter Value Range		
Spot size diameter:	10-22 mm		
Wavelength	1064 nm		
Fluence:	10-50 J/cm ²		
Laser pulse duration:	20-50 ms		
Rep. rate:	Up to 2 Hz		
DCD cooling	0-50ms		

Immediate Post-Treatment Procedure

1. Immediately after treatment the subject will be asked to rate the pain on a 0-10 (none to worst).

3. The subject will be instructed on post-treatment care.

Long Term Follow-Up Procedure

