- 1. Subjects will return to the study site for a one (1), three (3) and (6) month follow-up visits after the laser treatment.
- 2. The treatment areas will be photographed.
- 3. Tape measurements and weight will be recorded.
- 4. Ultrasound and skin elasticity measurements will be done if they were done at baseline.
- 5. A clinical evaluation of purpura, edema, erythema, hyperpigmentation, hypopigmentation, blistering and scarring will be assessed by the investigator using the following scale:

0 = absence

1 = mild

2 = moderate

3 = severe

- 6. At the follow-ups the subjects will be asked to evaluate their satisfaction with the treatments. They will be asked to complete the questions below. The first question will ask the subject to rate each treatment procedure using the following scale:
 - 1 = Not Satisfied
 - 2 = Little Satisfaction
 - 3 = Somewhat Satisfied
 - 4 = Satisfied
 - 5 = Very Satisfied
- 7. The subject will also be asked to rate the overall improvement in the appearance of their treated skin using the following scale:
 - 1 = No improvement
 - 2 = Little improvement
 - 3 = Moderate improvement
 - 4 = Significant improvement
 - 5 =Complete improvement
- 8. The subject will have the option to receive an additional treatment on the control side if the treatment results in asymmetric improvement of cellulite. They may have this option starting at the final follow-up.

SECTION 4: SUBJECTS (PERSONS/CHARTS/RECORDS/SPECIMENS)

A. Number of Subjects (Charts/Records/Specimens)

- Indicate the maximum number of subjects to be consented on this UCI protocol.
 - Include projected screen failures and early withdrawals.
 - For Mail/Internet surveys include the number of people directly solicited.
 - If the study involves use of existing charts, records, specimens, specify the maximum number that will be reviewed to compile the data or the sample population necessary to address the research question.

40

- 2. Of the maximum number of subjects listed above, indicate the **target sample size** for the study.
 - The target sample size is the number of subjects expected to complete the study or the number necessary to address the research question.
 - If the study only involves use of existing records, charts, specimens, specify the target number needed to address the research question.

24

Explain how the study sample size was determined (e.g., power analysis; review of related literature).

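### The blinded panel's 0-4 scale has no category for worsening, so the treated-minus-untreated efficacy score is compressed in both directions

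*Protocol*

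**What the plan says.** Protocol, Section 1, sets out the outcome. Three blinded evaluators compare pretreatment photographs with those from the 1, 3 and 6 month visits, and each "will rate improvement on the scale 0 to 4, as described below". The table has five rows: 0% scores 0, 1-25% scores 1, 26-50% scores 2, 51-75% scores 3 and 76-100% scores 4. Every row describes improvement or its absence. The section then defines the efficacy measure: "The difference scores between the treated and the untreated sides will be used to measure treatment efficacy".

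Other records bear on the point without entering that score:

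- **Photographs.** Pre-Treatment Procedure, item 8: "Photographs will be of the treated and control areas".
- **Body measures.** The study design text says "weight/height will be recorded and the Body Mass Index (BMI) will be calculated at baseline and follow-up visits". Long Term Follow-Up Procedure, item 3, says "Tape measurements and weight will be recorded".
- **Ultrasound and elasticity.** These are optional. Item 4 of the follow-up procedure says "Ultrasound and skin elasticity measurements will be done if they were done at baseline".
- **Investigator.** Section 1 says that the investigator's "assessments during follow-up visits will be tabulated and analyzed with basic descriptive statistical methods". What is assessed is not stated in the text available, parts of which were removed.
- **Subject.** Follow-up item 7 asks subjects to "rate the overall improvement in the appearance of their treated skin using the following scale". That scale runs from 1 to 5 and also starts at no improvement.

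**The concern.** The untreated side is there to show what happens without the laser, in either direction. A scale that stops at no improvement records only upward change, and the efficacy score is the difference of two scores truncated in this way. Four consequences follow:

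- Worsening of the treated side is understated.
- Worsening of the untreated side, which would count as relative benefit, is understated too.
- If a side improves in some subjects and worsens in others, only the improvements count, and the mean shifts in that side's favour.
- If both sides worsen, most of a real difference between them disappears.

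No other scale in the text available grades worsening of cellulite. The 0-3 safety scale covers purpura, edema, erythema, pigment change, blistering and scarring. Nurnberger-Muller staging is listed only before treatment. The protocol itself fixes both the categories and the efficacy measure, and no later analysis can restore a grade that the form did not allow.

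**Working it through.** **Inputs from the protocol.** The five bands and the difference score (Section 1), and a target of 24 subjects (Section 4A). The protocol gives no SD, effect size or rate of worsening, so there is no stated figure to reproduce. All shifts and SDs below are assumptions.

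**Step 1: error-free rating.** The comparison scale mirrors the printed bands below zero, from -4 to +4. The possible difference then runs from -8 to +8 instead of -4 to +4.

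| Treated change | Untreated change | Printed difference | Signed difference |
|---|---|---|---|
| -20% | 0% | 0 | -1 |
| 0% | -20% | 0 | +1 |
| -40% | -10% | 0 | -1 |
| +20% | -20% | +1 | +2 |
| -20% | +20% | -1 | -2 |
| +20% | 0% | +1 | +1 |

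**Step 2: rating error.** Assume that the perceived change on a side is normal with mean μ and SD σ, independent between sides, one rating per side. The cuts lie halfway between the printed bands, at 0.5, 25.5, 50.5 and 75.5. Then P(score k) = Φ((upper cut - μ)/σ) - Φ((lower cut - μ)/σ), and the mean score is Σ k·P(k).

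Example with σ = 15, treated 20 points worse, untreated unchanged:

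- Untreated (μ = 0): P(1) = 0.4421, P(2) = 0.0442, P(3) = 0.0004. Mean = 0.4421 + 2×0.0442 + 3×0.0004 = 0.53.
- Treated (μ = -20): P(1) = 0.0847, P(2) = 0.0012. Mean = 0.0847 + 2×0.0012 = 0.09.
- Printed difference: 0.087 - 0.532 = -0.44. Signed difference: -1.19 - 0 = -1.19.
- Standardised (difference over the SD of the difference): -0.44/√(0.082 + 0.340) = -0.68, against -1.19/√(0.743 + 1.245) = -0.85. The loss is 19.2%, computed before rounding.

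**Step 3: results for σ = 10 / 15 / 20.**

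| Mean change (treated, untreated) | Printed scale | Signed scale | Standardised loss |
|---|---|---|---|
| (-20, 0) | -0.47 / -0.44 / -0.43 | -1.25 / -1.19 / -1.13 | 19.2 / 19.2 / 17.5% |
| (-50, 0) | -0.49 / -0.53 / -0.59 | -2.48 / -2.48 / -2.47 | 57 / 52 / 46% |
| (-20, -40) | +0.02 / +0.08 / +0.14 | +0.83 / +0.88 / +0.93 | 87 / 64 / 48% |
| Treated half +25, half -25; untreated 0 | +0.26 / +0.23 / +0.20 | 0 | not applicable |
| (+10, 0) | +0.40 / +0.36 / +0.33 | +0.74 / +0.64 / +0.58 | 0.7 / 1.6 / 3.5% |
| (0, 0) and (-20, -20) | 0 | 0 | none |

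The mirror cases (0, -20) and (0, -50) have the same sizes with a positive sign. The ±25 mixture on the untreated side gives -0.26 / -0.23 / -0.20.

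The printed scale hardly separates 20 points of harm from 50. The treated side's mean score is already 0.02 to 0.16 at 20 points worse and can fall no further than 0. What remains of the difference is mostly the unchanged side's mean score of 0.49 to 0.60, which comes from rating error.

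**Step 4: direction at n = 24.** In 4,000 simulated trials with the mean of three raters, no between-subject variation (which flatters detection) and a paired t-test at 5%, the (-20, 0) harm was flagged in 100 / 100 / 99.5% on the printed scale and 100 / 100 / 99.9% on the signed scale. The (-20, -40) benefit was flagged in 4 / 72 / 84% on the printed scale against 100% on the signed scale.

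**Step 5: a second model.** The true change was given an SD of 15 or 25 points and a within-subject correlation of 0 or 0.5, with mean changes between -10 and +20. The printed mean difference was 0.44 to 0.63 of the signed one. The approximate power loss at 24 subjects was 0 to about 13 percentage points, the largest being 0.63 against 0.76 for (-10, 0) with SD 15 and correlation 0.5.

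**The case against.** The case on the other side accepts the missing category and disputes the consequence.

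- **The large losses need large worsening.** Nothing in the protocol suggests shifts of 40 or 50 points. Subjects have one laser treatment and a BMI below 27, weight is tracked and photography is standardised. In the same model a treated side 5 points worse costs 4-8% in standardised terms, and 10 points worse costs 7-11%. A ±15 mixture gives a bias of about 0.08 to 0.09, ±10 about 0.03 to 0.04, and ±5 about 0.01. This stands, and the size in this trial is unknown.
- **The printed scale is not always the weaker one.** For a 20-point benefit over an unchanged side it ranges from a 0.6% gain to a 1.6% loss. For a 30-point benefit it is about 1-11% more sensitive, because error around the unchanged side is truncated. This also stands and is a real cost of changing.
- **Raw comparisons such as -0.49 against -2.5 depend on the mirrored bands, which are a choice.** This is true. The standardised losses depend less on the units, and the zeros in Step 1 do not depend on them at all.
- **Photographs of both areas could be re-rated, and data are kept for about 5 years (Section 12).** This is correct. The information is lost from the scores, not from the study, but recovering it would take a second reading.
- **The investigator's assessment may record worsening.** This cannot be excluded, since its content is not visible. It is still not the efficacy score.
- **This is a pilot with no powered comparison.** That limits the seriousness. A pilot's effect size and SD are nevertheless what a later trial would use, and the floor distorts both.
- **The panel might rate the two sides jointly.** A difference of scores between sides implies a score for each, and a joint 0-4 improvement rating would have no worsening category either.

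**Conclusion.** The concern holds. As written, any worsening is scored 0 on either side, and the efficacy measure inherits that floor. Confidence in the missing category and in the compression is high. Confidence in its size in this trial is low, because every shift and SD above is assumed.

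Under rating error of SD 10-20 points, a 20-point harm beside a stable control appears at a little over a third of its signed size, with a standardised loss of 17.5-19.2%. Its direction is almost always kept. The more serious distortions are mixed responses, where a zero mean effect reads as +0.20 to +0.26 for ±25 points, and worsening on both sides, where 48-87% of the standardised difference goes. There is no bias when both sides share the same distribution of change, and a 10-point benefit over an unchanged side loses only 1-4%. The change should be made because it is cheap and the rating form is the only place to make it without a second reading. The defect does not invalidate the study.

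**What to change.** Replace the panel scale in Section 1 with wording such as:

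> For each side, on a blinded basis, every evaluator grades change since baseline from -4 to +4. Grades +1 to +4 are as tabulated; 0 is no change; -1 is 1-25% worse; -2 is 26-50% worse; -3 is 51-75% worse; -4 is more than 75% worse. The difference score is the signed treated score minus the signed untreated score. The number of sides rated worse is tabulated at each visit.

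Add a worse option to the subject's improvement question (Long Term Follow-Up Procedure, item 7).

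The cost is a revised rating form and one added option on the subject form, with the same three raters, photographs and visits. If ratings have already been made, the stored photographs would have to be read again. There are three drawbacks: results compare less directly with other 0-4 results; the lowest band is open-ended, because worsening has no natural 100% limit; and some sensitivity is lost if the treated side improves by about 30 points over a stable control. A single worse category would close the structural gap, but it would not show how much worse a side became.

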Treatment Procedure

The following table provides a summary of the required study visits, the procedures and assessments to be performed at each visit.

Assessments/ Procedures	Pre- Tx	Tx 1	Follow-up 1 month	Follow-up 3 months
Informed Consent	X			
History	X			
Inclusion/ Exclusion Criteria	X			
Subject No. Assignment Randomization	X			
Photography	X	X	X	X
Ultrasound/skin elasticity assessments (optional)	X	X	X	X
Non-invasive light measurements	X	X	X	X
Measurement (average of 3) / Weight	X		X	X
Laser treatments		X		
Assessments of side effects		X	X	X
Post-treatment care instructions		X		
Assessment			X	X
Subject Satisfaction survey			X	X

Pre-Treatment Procedure

- 1. Subjects will be recruited at the investigational site.
- 2. Prior to any screening assessments, informed consent will be obtained. When the subject fully understands the possible benefits and risks of the study, the subject will be asked to sign and date the informed consent form. The investigator will then sign and date the form. The subject will be given a copy of the completed consent form.
- 3. A detailed medical history will be obtained.
- 4. The subject will undergo a standard exam to determine if they meet the study criteria.
- 5. Skin type will be recorded using the Fitzpatrick classification of phototype.
- 6. Tape measurements of the treated area, height, and weight will be recorded.
- 7. The presence and severity of cellulite will be noted using the following 2 methods:

Nurnberger-Muller Scale:

- Stage 0: No dimpling. Pinch test "folds and furrows", no mattress like appearance.
- Stage 1: No dimpling. Pinch test reveals mattress like appearance.
- Stage 2: Dimpling spontaneously standing.

Stage 3: Dimpling spontaneously standing and lying down.

Texture Scale:

Hard or Solid: Pinch test "firm folds and furrows" mattress-like appearance. Adherent to deep planes. Not modified with lying versus standing position.

Soft or Flaccid: Pinch test "spongy and floating folds and furrows", mattress-like appearance. No adherence to deep planes. Not painful, flaccid. "Orange peel skin" appears spontaneously.

Edematous: Doughy consistency. Dimpling Spontaneously. Pain and cramps. Signs of venous and lymphatic insufficiency "legs in boot/column".

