- 1. Describe the **risks/potential discomforts** (e.g., physical, psychological, social, economic) associated with **each** intervention or research procedure.
- 2. Estimate the probability (e.g., chance or likelihood of occurrence) that a given harm may occur and its severity (e.g., mild, moderate, severe).

The possible risks and/or discomforts associated with the procedures described in this study include pain, purpura (bruising), edema, papule formation, erythema (redness), hyperpigmentation (darkening of skin), hypopigmentation (lightening of skin), blistering, crusting and scarring. Changes in the skin from any of the aforementioned risks may be temporary or permanent. A lesser possibility exists of pinpoint bleeding and infection associated with a wound from blistering or bleeding in the treatment area.

3. Discuss what measures have been taken and/or will be taken to **prevent and minimize** any risks/ potential discomforts.

The PI and colleagues have extensive experience in performance of laser treatments which will help to minimize risk. If hyperpigmentation occurs, bleaching cream can be used to minimize the effect.

- For Full Committee protocols, state whether any study procedures may involve risks to the subject (or embryo or fetus, if the subject is or may become pregnant) that are currently unforeseeable.
- [] Not applicable This study qualifies for Exempt or Expedited review.

It is possible that the laser treatment could involve risks that are currently unforeseeable. Because laser light penetrates only a few millimeters into the skin, risk to a fetus is unlikely. However, because the risk to a fetus is unknown, pregnant women will be excluded.

C. Potential Benefits

- 1. Discuss the benefits that may accrue **directly to the subjects**. *Note: Compensation is not a benefit. Do not include it in this section.*
- [] There is no direct benefit anticipated for the subjects.

The possible benefits from the procedures described in this study include improvement in the appearance of cellulite and/or tightening of thigh skin.

2. Describe the potential societal/scientific benefit(s) that may be expected from this study.

This study may allow us to provide better treatments for cellulite in the future.

[figure not shown]
D. Risk/Benefit Assessment

For **Expedited and Full Committee protocols**, explain why the study risks are reasonable in relation to the **potential benefits** to subjects and society.

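### The graded safety list omits four of the protocol's own named risks, and no assessment is scheduled between treatment day and month 1, so some events may go unrecorded

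*Protocol*

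**What the plan says.** **Safety outcome.** Section 1 of the protocol states: "Safety will be assessed by clinical evaluation of purpura, edema, erythema, hyperpigmentation, hypopigmentation, blistering and scarring". The investigator grades each sign from 0 (absent) to 3 (severe). The Long Term Follow-Up Procedure repeats the list and scale: "A clinical evaluation of purpura, edema, erythema, hyperpigmentation, hypopigmentation, blistering and scarring will be assessed by the investigator".

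**Named risks.** Section 7B says that the risks "include pain, purpura (bruising), edema, papule formation, erythema (redness), hyperpigmentation (darkening of skin), hypopigmentation (lightening of skin), blistering, crusting and scarring". It adds: "A lesser possibility exists of pinpoint bleeding and infection associated with a wound from blistering or bleeding in the treatment area". It also says that skin changes may be either temporary or permanent.

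**Timing.** In the visit table under Treatment Procedure, the row "Assessments of side effects" is marked for the treatment visit, month 1 and month 3. The Long Term Follow-Up Procedure adds month 6: "Subjects will return to the study site for a one (1), three (3) and (6) month follow-up visits after the laser treatment". The text available places no visit, call or diary between treatment day and month 1.

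**Pain.** This is rated separately by the subject, from 0 to 10, straight after treatment (Immediate Post-Treatment Procedure).

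**The concern.** Safety is half of the stated objective in Section 1, so the safety outcome should be able to report the harms that the protocol itself expects. Two features stand in the way.

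First, the graded list is shorter than the risk list. A harm with no line on the grid is recorded only if an investigator chooses to note it, and that may differ from subject to subject.

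Second, the grading is worded as an evaluation at the visit. Nothing in the available text asks what happened since the previous visit. The first interval, from treatment day to month 1, is the one in which a temporary reaction could come and go unseen.

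The stake is a safety table that shows few or no events partly because of what was asked and when. A statistical analysis plan cannot repair this afterwards, since it cannot recover events that were never recorded.

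**Working it through.** The protocol states no figure for safety, so there is none to reproduce. The check compares lists and dates.

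**1. Risk list against graded list**

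| Risk named in Section 7B | Where it is captured |
|---|---|
| Purpura, edema, erythema, hyperpigmentation, hypopigmentation, blistering, scarring | 0 to 3 grid (Section 1; Long Term Follow-Up Procedure) |
| Pain | 0 to 10 rating on treatment day |
| Papule formation, crusting | No grade in the text available |
| Pinpoint bleeding, infection | No grade in the text available |

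Count: 10 main risks + 2 lesser ones = 12. Then 12 − 7 graded = 5, and 5 − 1 (pain) = 4 without a grade.

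**2. Assessment times**

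Side effects are assessed on treatment day and at months 1 and 3 (visit table), plus month 6 (text). For a graded sign there are three cases around the first interval:

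- visible at the treatment-day assessment: can be recorded, even if healed by month 1;
- starts later and is still present at month 1: can be recorded;
- starts later and heals before month 1: not seen at either assessment.

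Only the third case is a gap. Let f be the share of events visible on treatment day, and g the share of the remainder still visible at month 1. If the plan records only what is seen at visits, the share missed is (1 − f)(1 − g). The documents give neither f nor g, so these values are assumptions that show the range:

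| f | g | Share missed |
|---|---|---|
| 0 | 0 | 100% |
| 0.5 | 0 | 50% |
| 0.5 | 0.25 | 37.5% |
| 1 | 0 | 0% |

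The result runs from nothing to everything, so no under-count can be stated.

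**3. Could an ungraded event plausibly occur in this trial?**

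The target sample size is 24 (Section 4A). For an assumed true rate p, the chance of at least one case is 1 − (1 − p)^24, and the expected number of cases is 24p:

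- p = 2%: 1 − 0.98^24 = 38%; 0.5 cases expected
- p = 5%: 1 − 0.95^24 = 71%; 1.2 cases expected
- p = 10%: 1 − 0.90^24 = 92%; 2.4 cases expected

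These rates are assumed, not taken from the protocol. They show only that an event of this kind could well arise at this sample size.

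**4. Which grades are summarised**

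Section 1 says that the investigator's follow-up assessments will be tabulated descriptively. It is unclear whether this includes the safety grades. If it does, the sentence does not mention the treatment-day grades.

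**The case against.** **Other adverse-event capture may exist in text that is not shown.** This stands. Part of the text before the study design is removed. The Immediate Post-Treatment Procedure goes from item 1 to item 3, and the part that should precede item B, Compensation for Injury, is absent. A reader might infer that the trial has no other adverse-event collection and would report no crusting, papules, bleeding or infection even if they occurred. The documents do not support that. The side-effects row in the visit table is also worded openly, and nothing forbids noting another reaction. But the only content given for that assessment is the seven-sign list, so capture of anything else is left to discretion.

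**Treatment day is covered.** This also stands. A reader might infer that every event healed by month 1 is missed, including immediate bruising, redness or swelling. The visit table rules this out for any graded sign visible on treatment day.

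**A risk list for an ethics board need not match an outcome list, and the omitted harms are minor.** This stands in part. Section 7B does call bleeding and infection a lesser possibility and ties them to blistering or bleeding, and blistering is graded. Papule formation and crusting, however, are in the main risk list beside the graded signs, and no reason is given for leaving them out. An infection that follows a wound also need not be visible on treatment day.

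**No under-count is shown.** Correct. One might cite the one-sided 95% upper bound for zero events in 24, 1 − 0.05^(1/24) = 11.7%. The protocol plans no such bound, and it reflects sample size, not incomplete recording, so it does not measure this problem.

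**Conclusion.** The point holds in a limited form. Two facts can be read directly from the protocol: four of its twelve named risks are absent from the graded safety list, and no side-effect assessment is scheduled between treatment day and month 1. It follows that the four ungraded harms, and any graded sign that both starts after the treatment-day assessment and heals before month 1, may go unrecorded. The safety summary may then be too favourable.

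This rests on two assumptions: that no further adverse-event collection is described in the parts not shown, and that some reactions do begin and heal within the first interval. The protocol allows for temporary changes but gives no onset or duration. The size cannot be derived from the documents, and a firm statement that harm is under-counted would go beyond them. The change is worth making because it is cheap and aligns the safety outcome with the protocol's own risk list.

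**What to change.** 1. Add papule formation, crusting, pinpoint bleeding and infection to the 0 to 3 grid, in Section 1 and in the Long Term Follow-Up Procedure.
2. At each follow-up visit, record two grades for every sign: the grade on that day, and the worst grade since the last assessment by subject report.
3. Tabulate the worst post-treatment grade per sign, including the treatment-day grade, as the safety summary.
4. If adverse-event collection is already described elsewhere in the protocol, refer to it from the safety paragraph in Section 1.

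**Cost:** four rows and one column on the form. No extra visit or staff is needed and treatment does not change. The downside is that interval grades depend on subject recall, so they should be reported as such, with the investigator's same-day grades kept separate.
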